Study Duration: Approximately 12 months total for this component. Analysis of PrEP (TAF vs TDF) drug levels will be completed within approximately three months after the last participant follow-up visit. The duration is shorter because we have ongoing cohort recruitment ongoing in Gugulethu, NY1 and Vuyani and can recruit 70 women who reside close to the clinic within 2-3 months.

Study procedures: Weekly (see **Table 2** for scheduled events), following PrEP initiation a maternal blood specimen will be collected via venepuncture (at home or in clinic, depending on participant's preference). This specimen will be used to create a DBS specimen to be tested at the laboratory at the University of Colorado. DBS cards will be prepared and stored following standard protocols and stored at -80°C for shipment and analysis at the end of the study with the clinical pharmacoanalytic laboratory of [name] at University of Colorado, Denver (funding proposal under separate cover).

Enrolled maternal participants can continue to take PrEP through delivery and postpartum period to prevent HIV during this time. Pregnancy and postpartum periods are associated with elevated risk for HIV acquisition. As such, the study aims to evaluate the different levels of TAF vs TDF associated with once-daily FTC/TDF regimen vs FTD/TAF regimen. Study staff will monitor and document maternal participants' daily administration of the study drug.

Only doses directly observed in-person or via video call by study staff or sent video recordings will be considered adequate documentation of the PrEP doses taken for the purposes of defining an evaluable participant (see Analytics).

These data will be used to determine the drug thresholds for understanding of TAF vs TDF adherence measures. The drug threshold corresponding to adequate adherence will be defined from the distribution of steady-state TFV-DP concentrations at antenatal vs postnatal visits.

If up to 3 PrEP doses were not directly observed, a urine test will be done to detect the presence of tenofovir metabolite in the participant's system prior to the drawing of blood samples.

We will evaluate the 'tail' (plasma and intracellular) of TFV and TFV-DP in the PrEP setting, comparing TAF to TDF and TAF and TDF levels in pregnant to postpartum women. See SOPs for dried milk spots (DMS) and dried blood spot (DBS) collection in Appendix.

- Plasma PK (TFV) – 8 samples in pregnancy, and 8 samples in postpartum (1 per week)

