- PBMC (plasma)- 2 samples in pregnancy and 2 in postpartum at weeks 4 and 8 (4 PBMC samples per participant=100 samples)
- Breastmilk PK for TAF and TDF arms – Given there are no data on TAF in breastmilk, we propose to conduct a single sample of DMS matched with plasma samples and compare to TDF samples.
1 sample x 40 participants (TAF and TDF arms) =40 tests at 4 hours after peak (week 8)
- Urine tests- Tenofovir rapid tests will be done as needed to verify the presence of tenofovir metabolites in those participants who have stated that they have taken their PrEP but were not observed doing so.

Video DOT : We will provide the option of sharing videos of taking PrEP daily (live) instead of coming to the clinic, which has been used in previous studies led by [name] and team, including IMPAACT 2009. Participants will also be asked a few questions around their experience and perceptions of taking video observed PrEP doses during an exit interview at their final study visit.

Homebased collection of specimens : In light of COVID-19 lockdown and complexity of plasma collection, we will offer homebased collection of DBS and DMS to women by a nurse who will travel to their homes for collection of samples as required.

The PK Component will establish PK parameters for TFV-DP under TFV vs TAF under adequate adherence during pregnancy and postpartum. This PK study is necessary because it will allow investigators to compare levels of TFV-DP in TAF vs TDF and to compare levels needed for optimal adherence in pregnancy vs postpartum periods.

Table 2: Schedule of events of PK study

Weeks	During third trimester								During postpartum period								
	B	1	2	3	4	5	6	7	8	1	2	3	4	5	6	7	8
Informed consent process	X																
Medical history	X																
Concomitant medication	X																
Gestational age	X																
Safety bloods*	X												X				
Complete blood count (CBC) with differential and platelets, HCT	X												X				
HIV test (4 th gen)	X				X					X			X				X
Randomise to TAF vs TDF	X																
Dispense PrEP	X			X				X					X				X
Observed daily PrEP dosing via video call	X	X	X	X	X	X	X	X		X	X	X	X	X	X	X	X
Plasma PK sampling (TFV)	X	X	X	X	X	X	X	X		X	X	X	X	X	X	X	X
DBS	X	X	X	X	X	X	X	X		X	X	X	X	X	X	X	X
PBMC					X					X			X				X
Breastmilk Sampling [^]																	X

*Creatinine, HepBSag, ALT, renal function panel (baseline and postpartum, 2 time points),

[^] For both TAF and TDF arms

ANALYTICS

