Primary Objective: To establish benchmarks of TFV-DP concentrations following daily dosing with TAF vs TDF in pregnancy and again in postpartum

Secondary Objectives: To compare the difference with TFV-DP with TDF and TAF for pregnancy against postpartum and to establish benchmarks of TFV-DP in breastmilk in postpartum women and compare with TDF arm.

Prior to conducting analyses, the study team, including the study Pharmacologists, will review the pattern of completeness of each participant's directly observed PrEP therapy (via video call) to ascertain if all 8 weeks were taken daily in antenatal and postnatal care to determine suitability for inclusion in the analysis. In each of the groups (TDF vs TAF in antenatal and postpartum groups), the distributions of steady state concentration (Css) defined as the TFV-DP concentration observed will be summarized.

For each group, we will plot median and interquartile range (IQR) TFV-DP concentrations for each week and fit a Loess curve and 95% confidence interval (CI) to the concentration-time data. The plateau in the concentration-time curve was assumed to represent steady-state. Tenofovir diphosphate at week 8 (steady-state) will be analyzed as median, IQR, mean, standard deviation (SD), and 95% CI in the pregnancy and postpartum groups by study arm. The Wilcoxon rank-sum test will be used to evaluate differences in the distribution of 8-week concentrations between groups. Additionally, a nonlinear mixed-effects population PK model will be fit to the TFV-DP data using a 1-compartment constant input model using Phoenix (Certara, Princeton, NJ). The model will be used to summarize PK parameters for both groups and between TDF and TAF arms.

Differences between the antenatal and postpartum group intra-individual comparison of plasma TDF concentrations will be evaluated using two sample t-tests. We will evaluate bio-equivalence in plasma TFV-DP between TAF and TDF in pregnant and postpartum women.

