 - 4) checks the study participant's name against the source document to confirm that blood is being drawn from the correct participant
 - 5) shows the study participant all the equipment s/he will use to draw the blood and explains the tests required at this study visit.
- The RN prepares the laboratory items specific for each study visit i.e. the required blood tubes, needles / lancets / specimen containers, requisition form, etc.
- The RN labels each specimen container/card with the participants study identification number.

Dried Blood Spot

- Dried blood spots (DBS) can be obtained from venous blood or by finger-prick depending on the protocol and visit.
- For venous blood DBS, the study RN can obtain blood as described above and use a disposable pipette to spot 50µL of whole blood onto DBS cards which are properly labelled with participant study identification number, visit number, etc. The number of spots collected will be outlined in the protocol.
- For finger-prick DBS:
 - The RN washes his/her hands and draws on gloves if wanted. The SCO/RN asks the study participant which finger they prefer to give blood from and the study participant exposes the finger.
 - The RN cleans the appropriate site with an alcohol.
 - The RN uses a lancet to prick the indicated finger of the participant. The lancet is disposed of in the sharps container.
 - The RN will spot blood from the pricked finger onto a properly labeled DBS card (the number of spots collected will be outlined in the protocol). The RN will avoid "milking" the finger to avoid pain and hematoma. A second finger prick may be required.
 - When blood spots collection is complete, the RN will apply a bandage to the participant's finger to stop bleeding and help prevent infection.
 - The SRN removes the gloves and disinfects his/her hands. Then s/he records the correct time of taking the specimens on the laboratory requisition forms or on the app, as appropriate.
- The DBS cards are allowed to dry. To achieve this:
 - The DBS circle should not be touched once blood is applied.
 - Spots should be air dried overnight (min. is 4 hours) without the flap over the spots and placed in a clean and dry location, which is protected from rodents, insects and direct sunlight.
 - When the blood has dried, the flap of the DBS should be tucked as indicated on the card.

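### Weekly plasma TFV draws have no set time after dose, yet pregnancy and postpartum plasma levels are compared by a t-test that ignores it

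*Combined protocol and SAP*

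**What the plan says.** Section 2 (Study procedures) lists plasma TFV sampling as "8 samples in pregnancy, and 8 samples in postpartum (1 per week", and Table 2 repeats the weekly schedule. Neither gives a pre-dose rule, an hour after dose or a window. Blood may be taken "at home or in clinic, depending on participant's preference".

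The same section states: "We will evaluate the 'tail' (plasma and intracellular) of TFV and TFV-DP in the PrEP setting", both between arms and between pregnancy and postpartum. ANALYTICS names the test: "Differences between the antenatal and postpartum group intra-individual comparison of plasma TDF concentrations will be evaluated using two sample t-tests". I read this as the measured analyte, plasma TFV. The text does not say which weekly samples enter the test.

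The one sampling time relative to drug intake belongs to breastmilk: "40 tests at 4 hours after peak (week 8". That specimen is a "single sample of DMS matched with plasma samples and compare to TDF samples".

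On recorded times, the SOP for DBS collection says that the nurse "records the correct time of taking the specimens on the laboratory requisition forms", but within the finger-prick steps. Study procedures has staff document each daily dose and does not mention the clock time. The population PK model in ANALYTICS is fitted to TFV-DP, so it does not deal with plasma timing.

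**The concern.** A plasma concentration depends on how long ago the last dose was taken. If the hours from dose to draw differ on average between pregnancy and postpartum, the raw contrast combines any pharmacokinetic change with a difference in sampling time, and the named test cannot separate them.

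The schedule itself allows such a difference. Week 8 postpartum has a timed milk sample with matched plasma, whereas week 8 of pregnancy has no timed draw. An evaluation of the plasma tail also needs time since dose as a variable, and the plan does not define one. At stake is whether the plasma comparison between periods can be interpreted.

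**Working it through.** The plan gives no figure for the effect of timing, so there is none to reproduce.

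**Inputs from the documents.** 8 plasma draws per period; at most 1 of the 16 with an implied time (postpartum week 8); a basis of 15 women per group, raised to 35.

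**Assumptions, because the documents are silent.** Plasma half-life h of 10 to 20 hours (12 and 17 hours in step 4), single-exponential decline after absorption, log-scale SD 0.4, two-sided 5% test.

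**1. Size of a shift.** A draw taken d hours later is lower by 1 − 2^(−d/h).

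| Later by | h = 10 | h = 20 |
|---|---|---|
| 4 h | 1 − 2^(−0.4) = 24% | 1 − 2^(−0.2) = 13% |
| 8 h | 1 − 2^(−0.8) = 43% | 1 − 2^(−0.4) = 24% |

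The size also depends on where in the interval the draws fall. On an illustrative two-phase curve (fast half-life 1.5 to 3 h, slow 17 h, fast share 30 to 70%), moving from 2 to 5 hours after dose lowers the level by 20 to 43%. Moving from 20 to 23 hours lowers it by about 11 to 13%.

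**2. Own-control design.** With log C = (woman's level) − (ln 2/h) × t, the mean within-woman difference is the true period effect minus (ln 2/h) × (mean t in pregnancy − mean t postpartum). The woman's level cancels, but the mean time difference does not. A paired t-test would carry the same bias.

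**3. The timed week-8 sample.** Suppose only that draw differs between periods, by 8 hours. If week 8 alone is analysed, the shift is the 24 to 43% above. If all 8 draws are averaged on the log scale, it is diluted to 8/8 = 1 hour: 1 − 2^(−1/20) = 3% to 1 − 2^(−1/10) = 7%. The answer depends on which samples are used, and the plan does not say.

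**4. Chance of a false difference.** Take a 3-hour systematic shift and no true effect. Bias b = 3 ln 2/h, SE = 0.4 × √(2/n), and the rejection rate is Φ(b/SE − 1.96) + Φ(−b/SE − 1.96).

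| n per period | SE | h = 12 (b = 0.173) | h = 17 (b = 0.122) |
|---|---|---|---|
| 35 | 0.096 | 44% | 25% |
| 15 | 0.146 | 22% | 13% |

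The nominal rate is 5%. These rates treat the two periods as independent, as the named test does. Correlation within women would change them, but not the bias.

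**5. Random timing only.** If draws fall uniformly from 2 to 22 hours after dose, the SD of time is 20/√12 = 5.77 h. This adds a log SD of 0.693 × 5.77/h, that is 0.40 (h = 10) or 0.20 (h = 20). With n = 15, the added standard error of the period contrast is:
- averaging 8 draws per period: 0.40 × √(2/8)/√15 = 0.05, or 0.03 with h = 20;
- one draw per period: 0.40 × √2/√15 = 0.15, or 0.07 with h = 20.

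**The case against.** The strongest reply is that no systematic shift is documented. The choice of home or clinic is not tied to a period, and the separate home-collection offer names DBS and milk spots, not plasma. A reader might infer clinic draws in pregnancy and home draws postpartum, but the documents do not say so. Without a shift the harm is noise, and step 5 shows that it is modest if all weekly draws are averaged. This stands: bias is a risk that the plan leaves open, not an established fact.

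A reader might also infer that a few hours' shift could reproduce the pregnancy effect of 31 to 37% cited in the Introduction. The documents do not support this. That figure is for TFV-DP in red blood cells, and no plasma effect is given. Under the assumed half-lives, a 31 to 37% drop needs h × log2(1/(1 − x)) hours: 5.4 to 6.7 at h = 10, and 10.7 to 13.3 at h = 20.

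Nor is bias between TAF and TDF shown. The arms are randomised and share one schedule, and the bio-equivalence sentence names TFV-DP, not TFV.

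Finally, the primary and secondary objectives, the week-8 summaries, the Wilcoxon test and the population PK model all concern TFV-DP. The plasma test is ancillary, which limits the weight of the point. The milk time can be read as relative to a nominal peak, but the hour of that peak is not stated.

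**Conclusion.** The point holds for the pregnancy-postpartum plasma TFV comparison. No time after dose is set for the weekly draws, the named test ignores it, and nothing else in the plan corrects for it. The one implied time applies only to the postpartum period.

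The possible size is a 13 to 24% lower level for a 4-hour later draw and 24 to 43% for 8 hours, on an assumed half-life of 10 to 20 hours and single-exponential decline. Bias requires a systematic difference between periods, which the documents neither show nor prevent. The TFV-DP objectives are not affected. The change is worth making because it puts a better analysis in place of a stated one at small cost, and because dose times not captured during conduct may be impossible to recover.

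**What to change.** 1. Record the clock time of the last observed dose and of the draw for every plasma and milk sample. The documents mention a draw time only in the finger-prick DBS steps and no clock time for doses, so this needs a small CRF change as well as analysis wording.
2. Replace the two-sample t-test with a within-woman mixed model of log plasma TFV, using all timed weekly samples. Include period, arm, their interaction and time since dose. Check whether the decline with time differs by period; if it does, report the contrast at a stated time. A plasma PK model using actual times is an acceptable alternative.
3. If feasible, apply the same collection window in both periods. Adjustment relies on extrapolation if the sampling times of the two periods barely overlap.
4. State the milk sampling time in hours after the observed dose, and say whether its matched plasma is the weekly week-8 draw.

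The cost is a little extra recording. Samples without a timed dose drop out of the adjusted plasma analysis, and their number should be reported by period.

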Eligible, consenting women will receive up to R250 (~\$15) in grocery vouchers, transportation and refreshments per weekly visit for their time and effort in the study as well as transportation to the facility. All participants will also receive data bundles of 1GB at enrolment and 10GB every month thereafter for the duration thri follow up to send videos of them taking daily PrEP. During weekly visits, participants will receive minor refreshments (e.g. sandwich and cool drink).

Procedures for the informed consent process are outlined below. Throughout, trained study staff will ensure that women are aware of their right to refuse and/or withdraw from the study at any time. In addition, study staff will emphasize that all study activities are entirely separate from routine ANC and postnatal care services received and that refusal or withdrawal from the study will have no impact on their ability to access any services provided at any public-sector health facility.

Trained study counsellors will recruit n=70 women that are 20-30 weeks pregnant and NOT part of the ongoing PrEP-PP study for the PK sub-study. Participants will be screened for HIV infection; only those who test negative will be eligible to initiate once-daily FTC/TDF or FTC/TAF for PrEP. Participants must be willing to initiate and take PrEP and to take videos and send to the study for daily adherence for 8 weeks in pregnancy and again for 8 weeks postpartum. Women will be invited to participate in the study through ~2-3 months postpartum (depending on when they start the 8 week postpartum DOT). Women will be randomized into the TDF vs. TAF arm. Women will provide their own controls, providing pregnant and postpartum samples.

- **TDF Arm :** Women will receive a fixed dose combination of 200 mg emtricitabine (FTC) and 300 mg tenofovir disoproxil fumarate (TDF) administered once daily under direct observation for 8 weeks during pregnancy and again for 8 weeks in postpartum period
- **TAF Arm:** Fixed dose combination of 200 mg emtricitabine (FTC) and 25 mg tenofovir alafenamide (TAF) administered once daily under direct observation for 8 weeks during pregnancy and again for 8 weeks in postpartum period
- **At study end:** Participants in both arms will be given a 3 months supply of Tenemine (FTC200mg/TDF300mg).

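### Table 2, as extracted, marks no pregnancy week-8 plasma, DBS or PBMC sample, although the text analyses week-8 TFV-DP in both periods; check the printed table and reconcile

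*Combined protocol and SAP*

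**What the plan says.** In section 2, ANALYTICS, the summary measure is set at one time point: "Tenofovir diphosphate at week 8 (steady-state) will be analyzed as median, IQR, mean, standard deviation (SD), and 95% CI", for the pregnancy and postpartum groups by study arm. The test uses the same time point: "The Wilcoxon rank-sum test will be used to evaluate differences in the distribution of 8-week concentrations between groups".

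In section 2, Study procedures, sampling is weekly and starts after the first dose: "following PrEP initiation a maternal blood specimen will be collected via venepuncture", and that specimen also supplies the DBS. The plasma count is "8 samples in pregnancy, and 8 samples in postpartum (1 per week". The PBMC count is "2 samples in pregnancy and 2 in postpartum at weeks 4 and 8". Study procedures refers the reader to Table 2 for the scheduled events.

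The arm descriptions under Enrolment procedures give the dosing period as "administered once daily under direct observation for 8 weeks during pregnancy and again for 8 weeks in postpartum period".

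Table 2 has 17 time columns: B and weeks 1 to 8 in pregnancy, then weeks 1 to 8 postpartum. In the extracted text, the row "Plasma PK sampling (TFV") is marked at B and weeks 1 to 7 in pregnancy and at weeks 1 to 8 postpartum. The DBS and observed-dosing rows are identical to it.

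**The concern.** The prose reads naturally as samples at weeks 1 to 8 in each period. Table 2 reaches its eight pregnancy samples by counting B and stopping at week 7. Women are to be free of PrEP for the previous 90 days, re-enrolled women excepted, so a draw before the first dose would normally carry no information on accumulation.

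Table 2 is the schedule that sites work from. If it is printed as extracted, the pregnancy half of the primary benchmark has no sample scheduled at its defined time point, and a draw that is not taken cannot be recovered later. The likely substitute is week 7. The period comparison would then set seven weeks of accumulation in pregnancy against week 8 postpartum. The error would push the pregnancy value down, the same direction as the 31-37% pregnancy deficit cited in section 1.1.

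**Working it through.** **1. Count the marks.** Columns: 1 + 8 + 8 = 17. Splitting each row of Table 2 by cell gives:

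| Row | Pregnancy | Postpartum | Text elsewhere |
|---|---|---|---|
| Plasma | B, 1-7 (8 marks) | 1-8 (8 marks) | 8 + 8, one a week |
| DBS | B, 1-7 (8) | 1-8 (8) | weekly, after initiation |
| Observed dosing | B, 1-7 (8) | 1-8 (8) | 8 weeks in each period |
| PBMC | 4 (1) | 1, 4, 8 (3) | weeks 4 and 8 in each period (2 + 2) |
| HIV test | B, 4 | 1, 4, 8 | baseline and monthly (Table 1) |
| Dispensing | B, 3, 7 | 4, 8 | not stated by week |

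The plan's own figure of 8 + 8 plasma samples is reproduced. No row has a mark at pregnancy week 8.

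**2. What the count settles.** The plasma row has 16 marks in 17 columns, so one cell is blank. If B is truly marked, 8 - 1 = 7 pregnancy samples follow baseline. Marking B and all sixteen weeks would need 17 marks. If the eight pregnancy marks belong one cell to the right, they fall at weeks 1 to 8, the blank is at B, and table and text agree. The total alone cannot tell these apart.

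**3. Which columns can be trusted.** Consent and randomisation fall in B. PBMC falls at pregnancy week 4 and postpartum weeks 4 and 8, as the text says. The single breast-milk mark falls in the last column, week 8, again as the text says. These fix the grid away from the period boundary. At the boundary there are signs of displacement:
- The postpartum heading begins over pregnancy week 8, one column too far left.
- The PBMC mark at postpartum week 1 is one column right of pregnancy week 8. Moving it one cell left gives the 2 + 2 of the text.
- The HIV-test row has the same mark at postpartum week 1.
- Dispensing falls at 3 and 7 in pregnancy but 4 and 8 postpartum, as a one-cell left shift of the pregnancy block would produce.

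These shifts run in different directions, so the printed table cannot be reconstructed from the extracted text.

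**4. Size of the error if week 7 replaced week 8.** Assume first-order accumulation from zero, with half-life h in days. The fraction of plateau at day t is 1 - 2^(-t/h). Week 7 is day 49 and week 8 is day 56. The documents give no half-life, so h is an assumption.

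| h (days) | Week 7 | Week 8 | Ratio | Deficit |
|---|---|---|---|---|
| 7 | 0.992 | 0.996 | 0.996 | 0.4% |
| 14 | 0.912 | 0.938 | 0.972 | 2.8% |
| 17 | 0.864 | 0.898 | 0.963 | 3.7% |
| 21 | 0.802 | 0.843 | 0.951 | 4.9% |
| 28 | 0.703 | 0.750 | 0.937 | 6.3% |

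For h of 14 to 21 days the deficit is about 3-5%. It concerns the pregnancy value only, so it does not depend on the level at which a woman starts the postpartum block. A woman who began pregnancy dosing above zero would show a smaller deficit.

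**The case against.** The strongest reply is that this is a fault of the extracted table and not of the plan. The grid shows displacement at exactly these columns, and the prose provides the sample: weekly after initiation, eight per period, PBMC at pregnancy week 8, and an analysis at week 8. This stands to the extent that an omission is not established. It does not remove the query, because the same gap appears in three separate rows whose first and last columns are fixed by other rows.

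A second reply is that B may denote dosing week 1. Table 1 lists directly observed dosing on days 1 to 7 among the procedures at entry, and the observed-dosing row has eight pregnancy marks for eight dosing weeks. Column 7 would then be the eighth dosing week, and the seven-against-eight contrast would not arise. This is possible. Even so, the postpartum block has no B, so the same dosing week would carry different labels in the two periods, and a draw on the day of consent and randomisation would be at or near the first dose.

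A third reply is that the Loess curves and the population PK model use all the weekly data and do not depend on a week-8 draw. That stands. Only the week-8 summaries and tests are exposed.

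A reader might infer that the mark count proves the omission however the cells are aligned. It does not: whether the blank lies at B or at week 8 is an alignment question. A reader might also infer that the missing PBMC mark is further proof. All four PBMC marks are present, one of them in a neighbouring region of the table, which is also what displacement would look like.

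**Conclusion.** Table 2 as extracted conflicts with Study procedures and ANALYTICS over the pregnancy week-8 sample. The conflict is credible enough to require a check of the printed table, and a correction if it is confirmed. I rate it should-fix, conditional on that check.

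It would be tempting to conclude that the primary endpoint is missing for all 70 women in pregnancy. The documents do not support that. It would require the printed table to match the extraction, B not to mean dosing week 1, and sites to follow the table over text that points to a week-8 draw.

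If the gap is real and week 7 is used, the loss is about 3-5% of the pregnancy value under assumed half-lives of 14 to 21 days and first-order accumulation from zero. That is small against the cited 31-37%, but it lies in the same direction and is avoidable.

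**What to change.** Check the printed Table 2 first, covering the plasma, DBS, PBMC, observed-dosing, HIV-test and dispensing rows. If the gap is confirmed:

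- Mark plasma, DBS and PBMC at pregnancy week 8.
- Do not count a pre-dose baseline draw among the eight weekly samples. Either drop it, or label it as an additional pre-dose sample and correct the sample count in Study procedures.
- Define week numbers by days of observed dosing, in the same way in both periods, so that week 8 has one meaning throughout. If B is meant as dosing week 1, say so and renumber.
- Reconcile the observed-dosing row with the eight weeks stated in the arm descriptions, and the HIV-test row with Table 1.

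The cost is a table correction and a line of text. If the baseline draw is kept, it adds at most one draw per woman, or 70 x 1 = 70 draws in all.

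### The additional population PK model assumes uninterrupted daily input and makes no use of the dosing record, so its parameters are biased if women with missed doses are modelled

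*Combined protocol and SAP*

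**What the plan says.** The Analytics section states that "a nonlinear mixed-effects population PK model will be fit to the TFV-DP data using a 1-compartment constant input model", and that "The model will be used to summarize PK parameters for both groups and between TDF and TAF arms". It does not list the parameters, and half-life is not named.

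Both arms are dosed "administered once daily under direct observation for 8 weeks during pregnancy and again for 8 weeks in postpartum period", which is 56 scheduled doses per period. Study procedures (section 2) adds that "Study staff will monitor and document maternal participants' daily administration of the study drug". The use given to that record is eligibility for analysis: only doses seen in person, by video call or on a sent recording "will be considered adequate documentation of the PrEP doses taken for the purposes of defining an evaluable participant". That sentence points to Analytics for detail. Analytics provides a review by the team and its pharmacologists "to ascertain if all 8 weeks were taken daily in antenatal and postnatal care to determine suitability for inclusion in the analysis", with no minimum number or percentage of doses.

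Study procedures also allows for gaps in observation: "If up to 3 PrEP doses were not directly observed, a urine test will be done" before blood is drawn. The period over which the three doses are counted is not stated. The urine-test item in the same section describes the test as serving women who say they took a dose that nobody saw.

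Separately from the model, Analytics defines Css as the observed TFV-DP concentration, summarises week-8 values directly, and compares week-8 distributions by Wilcoxon test.

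**The concern.** A constant-input model has no term for a day without a dose. A dip caused by a gap must be absorbed by the two quantities it can move: the plateau and the rate of approach to it. The plan collects the information that would prevent this but assigns it only to deciding who is evaluable.

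Two uses of the model are exposed. The primary objective is a benchmark under daily dosing, and a plateau distorted by missed doses is not that benchmark. The secondary objective compares pregnancy with postpartum in the same women. If dosing is less complete in one period than in the other, the model reports part of that difference as pharmacokinetics.

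**Working it through.** The documents give no half-life, expected rate of missed doses or model-based Css, so there is no stated figure to reproduce. The check asks what the specified model returns when doses are missing.

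**Inputs from the plan.** One compartment; once-daily dosing for 56 days; weekly samples, taken as days 7, 14, ..., 56; three doses as the size of the gap. Three of 56 is 5.4%.

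**Assumptions.** Half-life (t½) of 10, 14, 17 or 21 days; the position of the gap; doses placed mid-day-interval; no noise; one woman's profile at a time, fitted by least squares. This is not the full mixed-effects fit.

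**Formulas.** With k = ln 2 / t½, and doses scaled so that the true Css under full dosing is 1:
- generated data: C(t) = sum over doses taken before t of k·exp(−k(t − t_dose))
- model fitted: C(t) = Css·(1 − exp(−kt))

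**Step 1, complete dosing.** The fitted Css is within 0.2% of truth, and half-life is recovered. Constant input is adequate here.

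**Step 2, closed-form check at t½ = 17 days.** The full week-8 level is 1 − 2^(−56/17) = 0.898. Missing the last three doses removes 1 − 2^(−3/17) = 0.115, and 0.115/0.898 = 12.8%. Missing the first three removes 2^(−53/17) − 2^(−56/17) = 0.115 − 0.102 = 0.013, or 1.5%. These are changes in the observed value. They arise whichever model is used.

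**Step 3, fitted constant-input model, three doses missed** (change from the fit under full dosing; the spread row uses doses 11, 29 and 47):

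| Gap | Quantity | 10 d | 14 d | 17 d | 21 d |
|---|---|---|---|---|---|
| Last three | Css | −7.1% | −8.3% | −9.2% | −10.5% |
| | half-life | −16.1% | −16.1% | −16.5% | −17.1% |
| First three | Css | +6.1% | +9.9% | +13.2% | +18.1% |
| | half-life | +39.0% | +40.6% | +43.5% | +48.6% |
| Spread | Css | −5.9% | −6.3% | −6.6% | −6.9% |
| | half-life | −2.8% | −3.0% | −3.2% | −3.4% |

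**Step 4, other patterns.** With 90% of doses taken uniformly, Css is 10% low and half-life is unbiased. Doses missed at random at a rate of 3/56 (t½ 14 to 21 days) give a mean Css about 5% low and a median half-life within 0.4% of truth, although individual half-life fits run from about −20% to +31% (5th to 95th percentile).

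**Step 5, period contrast.** Suppose that pharmacokinetics are identical, pregnancy dosing is complete, and the last three postpartum doses are missed. The fitted postpartum-to-pregnancy Css ratio is then 1 − 0.105 = 0.895 to 1 − 0.071 = 0.929 instead of 1. For scale, the background section cites pregnancy levels 31% to 37% below postpartum.

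**Step 6, remedy.** Fitting the last-three profiles with input only on the days dosed returns Css of 1 and the true half-life at all four values.

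**The case against.** The strongest reply is that the plan already controls for this. A pharmacologist-led review looks at whether every day of the eight weeks was dosed, and only observed doses count towards evaluability. If only complete records pass, constant input is sound, as step 1 shows. That stands as a condition, but the plan does not say that only complete records pass. The review has no threshold, and Analytics does not supply the evaluability definition that Study procedures refers to.

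A second reply is that an unobserved dose is not a missed dose. That is correct, and the plan does not say that women with known missed doses will be analysed. A positive urine test, however, shows that drug is present. It does not show which of up to three doses was taken.

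Third, the model is supplementary. This stands in full. The observed Css and week-8 summaries and the Wilcoxon test do not depend on it.

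Some stronger readings are tempting and are not supported:
- That every dose is individually documented. The plan itself provides for unobserved doses.
- That any gap lowers Css and shortens half-life. Early gaps do the reverse, and evenly or randomly timed ones leave the typical half-life almost unchanged.
- That doses will be missed late in a period, or more often after birth. Nothing in the documents says so.

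**Conclusion.** The concern holds conditionally. The specified model cannot represent a missed dose, and the plan's screen does not clearly exclude women who have missed doses. Under half-lives of 10 to 21 days, a three-dose gap moves an affected woman's fitted Css by between −11% and +18%, and her half-life by between −17% and +49%, according to timing. If completeness differs by period, the model cannot separate adherence from pharmacokinetics.

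The half-lives and gap patterns are assumptions, and half-life is not a named output of the plan. The figures are for single noise-free profiles. The effect on a group estimate would also depend on how many women are affected and on how their gaps are timed.

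A reader might infer that the choice of model biases the study's main results. It does not: the observed summaries are untouched by it. Missed doses do lower observed week-8 values (by 11% to 19% when the last three are missed), but that is a matter of who is included. This is a worthwhile, inexpensive improvement to a supplementary analysis.

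**What to change.** Keep the one-compartment structure and replace constant input with each woman's recorded dosing history: a dose event on each day documented as taken, and none on days known to be missed. Run unobserved doses once as taken and once as not taken, and report both. Report Css as the model's prediction under full daily dosing, by arm and period, so that the benchmark refers to the stated regimen. Constant input may be kept alongside for women with complete observation, where the two should agree.

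State the numeric completeness rule that the pre-analysis review will apply, so that the reader knows which records reach the model.

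The cost is merging the dosing log with the concentration data and modest extra modelling. No new visits, samples or data are needed, and nothing is lost if dosing proves complete.
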